Feasibility and Acceptability of a Beverage Intervention for Hispanic Adults

NCT02911753 (ClinicalTrials.gov)

Registered September 19, 2016. Last updated November 1, 2017

Aims and Study Hypotheses

This pilot study will expand on earlier research by our team using beverage interventions to enhance cardiometabolic health. This study's primary objective is to assess the feasibility and acceptability of a beverage intervention in obese Hispanic adults. Primary feasibility outcomes will be recruitment, retention, and acceptability. Beverage intake will also be assessed through intake diaries and beverage return rates during weekly clinic visits. The preliminary efficacy of the beverage intervention will assess changes in total cholesterol, high-density lipoprotein (HDL), and low-density lipoprotein (LDL) over 6-weeks. Secondary outcomes are changes in fasting glucose, hemoglobin A1c (HbA1c), and high-sensitivity C-reactive protein (hs-CRP). Our study will evaluate participant-reported tolerance and as an exploratory aim, our study will also assess safety/toxicity-related to renal and/or liver function as albeit limited, evidence from green tea polyphenol E supplementation studies have reported a few cases of hepatic toxicity with on-going supplementation [1]. Renal and hepatic toxicity function will be assessed at baseline and 6-weeks. The aforementioned outcomes will be examined to test the following hypotheses: a) recruitment and retention of obese Hispanic participants in a 6-week beverage intervention study is feasible; b) the consumption of green tea and Mediterranean lemonade will be well-tolerated with high adherence; and c) green tea and Mediterranean lemonade intake will result in an improved cardiometabolic profile at the end of 6-weeks.

Design and Methodology

Design

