Potential risks may include but are not limited to: nausea, vomiting, frequent bowel movements, flatulence (gas), acid reflux, excess burping, heartburn, and bloating. If a participant experiences any of these signs/symptoms associated with beverage intake, they will be given the option to withdraw from the study or change to the alternate beverage intervention (but not flavored water) after a 1-week washout period. Participants will be asked on a weekly basis about any issues related to their beverage consumption and this information will be noted. Prior literature has reported a few cases of hepatic toxicity related to supplementation with high-dose green tea polyphenols [1]. No evidence exists to suggest toxicity or safety issues related to the green tea nor Mediterranean lemonade beverages consumed in the amounts prescribed for this study.

Therefore, renal and hepatic function will be monitored at study beginning and end using alanine transaminase (ALT) or aspartate transaminase (AST) values. Abnormal values will be shared with the participant and the participant will be advised to visit their physician for evaluation. In the event this occurs, participants will not receive additional compensation and the study will not cover additional costs for physician follow-up.

Methods for Assessing Study Outcomes and Potential Confounders

Anthropometry

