At the completion of the study, participants will take part in an exit interview where they will be asked to rate their overall satisfaction with the intervention, if they would consider a longer-term beverage intervention, and finally, if they would recommend the program to others. Participants will also be asked questions regarding satisfaction with their overall progress and for changing dietary beverage habits. Each item will be rated on a Likert scale with higher scores indicating greater program favorability. Open-ended questions will be used to seek participant input on modifications that could be made to improve acceptability and effectiveness of the intervention.

The responses will be used to identify which recruitment and intervention components were well received, which could be improved, and which were not acceptable.

Efficacy Outcomes

Descriptive statistics, including means, ranges, and standard deviations, will be calculated for the primary efficacy outcomes, cholesterol/lipid levels, and the secondary outcomes: fasting glucose, HbA1c, and hs-CRP. Mixed models will be used to compare arms in each of these outcomes' change from baseline. We will include fixed effects of intervention arm, time and their interaction to allow for different patterns of change between the arms, as well as a random participant effect to account for the longitudinal nature of the data. Baseline values of the outcomes will be included in the dependent variable vector. The changes from baseline, and the differences between arms in change from baseline will be estimated using contrasts from the mixed models. Mixed models yield unbiased estimates for data that are missing completely at random (when missingness does not depend on any observed or unobserved data) and missing at random (when missingness may depend on observed data, such as the baseline value of the outcomes), as these models perform an implicit imputation [12, 13]. Data from all patients who are randomized will be analyzed in the arm that they were randomized to.

Sample Size Calculation

The total sample size of 50 will provide 95% confidence intervals for the primary feasibility outcomes (proportion of eligible participants who enroll and the proportion of participants retained in the study) that are no wider than 0.28 (\pm margin of error = 0.14), conservatively assuming a base proportion of 0.5, which maximizes the standard error. The trial will be

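### Acceptability is rated only in an exit interview at study completion, so no rating is planned for participants who leave, and the results may look too favourable

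*Combined protocol and SAP*

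**What the plan says.** All references are to the combined protocol and SAP.

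- **Status of the outcome.** Aims and Study Hypotheses: "Primary feasibility outcomes will be recruitment, retention, and acceptability". The Feasibility outcomes part of the Statistical Analysis Plan names only recruitment and retention as primary.
- **How it is measured.** The Treatment Satisfaction/Acceptability section says: "At the completion of the study, participants will take part in an exit interview where they will be asked to rate their overall satisfaction". On scoring, it says: "Each item will be rated on a Likert scale with higher scores indicating greater program favorability". Open-ended questions on possible changes are added.
- **What it is for.** Same section: "The responses will be used to identify which recruitment and intervention components were well received, which could be improved, and which were not acceptable".
- **What happens to participants with symptoms.** Under Participant-Reported Tolerance or Toxicities, "they will be given the option to withdraw from the study or change to the alternate beverage intervention (but not flavored water"; the change of drink comes "after a 1-week washout period".
- **What is recorded earlier.** Study Intervention and the tolerance section describe weekly journals, measured returns, short check-ins about barriers, and weekly questions about problems with the drink. None is described as collecting the satisfaction items.
- **Retention.** Feasibility outcomes defines it as completers out of those enrolled. Sample Size Calculation calls the trial feasible if more than 70% are retained.
- **Six-week tests.** Blood is drawn at baseline and 6 weeks. Efficacy Outcomes analyses everyone randomized in the assigned arm. For safety, "Renal and hepatic toxicity function will be assessed at baseline and 6-weeks". No early-termination visit or recall of leavers is described.

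**The concern.** The participants most likely to find a drink unacceptable are those with symptoms, and they are offered a way out before the only acceptability measurement. Yet the responses are meant to show which components were not acceptable. If leavers liked the drink less than completers did, the reported ratings overstate how acceptable it was, and the team would carry that picture into a larger trial. A rating not taken when someone leaves cannot be reconstructed later.

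A secondary gap has the same cause. The efficacy analysis is meant to include everyone randomized, but nothing says how a 6-week lipid value would be obtained from someone who has left.

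**Working it through.** **1. The plan's own figures.** Inputs from Sample Size Calculation: n = 50, 95% confidence, p = 0.5, cutoff 70%. The half-width is 1.96 × √(p(1 − p)/n). At p = 0.5 it is 0.1386, so the width is 0.277, which agrees with the stated limit of 0.28. At p = 0.81 the half-width is 0.1087 and the lower limit 0.7013, just above 0.70 as stated. These figures are not in dispute.

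**2. Who can give a rating.**

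| Participant | Weekly records | Exit rating planned? |
|---|---|---|
| Completes on assigned drink | yes | yes |
| Switches drink, then completes | yes | yes, once, at the end |
| Withdraws | until leaving | none described |

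**3. Most participants unrated in a trial judged feasible.** Take the 50 randomized as the denominator and assume that every completer is interviewed. Since 35/50 = 0.70 is not greater than 70%, the smallest passing count is 36/50 = 0.72. That leaves 14/50 = 28% unrated. At 41/50 it is 9 (18%), and at 45/50 it is 5 (10%). These counts cover leaving for any reason, not only symptoms.

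**4. Effect on a mean rating.** Let r be retention, and C and L the mean ratings of completers and leavers. The mean in all randomized is rC + (1 − r)L. The completer mean therefore overstates it by C − [rC + (1 − r)L] = (1 − r)(C − L). The documents give neither the scale length nor the gap, so a 5-point item and gaps of 0, 1 and 2 points are assumed.

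| Retained | Gap 0 | Gap 1 | Gap 2 |
|---|---|---|---|
| 36/50 | 0 | 0.28 | 0.56 |
| 41/50 | 0 | 0.18 | 0.36 |
| 45/50 | 0 | 0.10 | 0.20 |

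**5. Effect on a percentage satisfied.** If a share s of completers is satisfied, the share in all randomized lies between rs (no leaver satisfied) and rs + (1 − r) (every leaver satisfied). The value of s is also assumed.

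| Retained | s = 80% | s = 90% | s = 100% |
|---|---|---|---|
| 36/50 | 57.6% to 85.6% | 64.8% to 92.8% | 72% to 100% |
| 41/50 | 65.6% to 83.6% | 73.8% to 91.8% | 82% to 100% |
| 45/50 | 72% to 82% | 81% to 91% | 90% to 100% |

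The width of each range is simply the unrated share.

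**6. Lipids.** The mixed model puts baseline values in the outcome vector. A leaver with no 6-week sample contributes the baseline value only, and validity then rests on missing at random. Symptoms are not among the model terms listed. The model is specified for lipids, glucose, HbA1c and hs-CRP, not for the exit ratings.

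**The case against.** The best defence has four parts.

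*The plan is silent rather than exclusive.* It never limits the interview to completers or bars contact with leavers, and Retention Strategies provides for family contacts, reminders and incentives. This stands as far as it goes: a reader might infer that leavers are shut out, and the text does not say so. The supported statement is that no rating, and no 6-week visit, is planned for them.

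*Nothing formal depends on the ratings.* A reader might infer that the feasibility verdict is biased. It is not: there is no acceptability threshold, the numeric retention rule is unaffected, and withdrawals count against it. Nor is a between-arm comparison of ratings planned, so unequal losses would not distort any planned test.

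*Tolerance is captured elsewhere.* This is largely right. Weekly records show symptoms, barriers and intake until a participant leaves. They do not supply satisfaction, willingness to continue for longer, or willingness to recommend.

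*One rating from a switcher is coherent.* A reader might infer that it is uninterpretable because it covers two drinks. The items concern the programme as a whole, and a permitted switch is part of that programme. A rating of the assigned drink at the switch adds information; it does not repair an error.

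A further tempting step is to say that a 6-week visit for leavers would restore the liver safety data. The tolerance section says "renal and hepatic function will be monitored at study beginning and end", but someone who stops after week 1 would be tested about five weeks (6 − 1) after the last drink. That says little about liver function when symptoms occurred, and the aim is exploratory.

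**Conclusion.** The point holds in a limited form. Followed as written, the plan yields acceptability ratings from completers only, for an outcome that the Aims section calls primary. Up to 14 of 50 (28%) could be unrated in a trial that still meets the retention rule. The direction is probably favourable to the drinks, if leavers liked them less. The size is unknown: the withdrawal rate, the scale length, the share satisfied and the completer-leaver gap in the working are all assumptions, and 28% is the boundary case rather than a forecast. With no leavers, or no gap, the ratings are unbiased.

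The consequence is a possibly rosy description used to refine the intervention. It does not produce a wrong feasibility decision. The change is still worth making because it is cheap and the information is lost if not collected at the time. The missing 6-week lipids are a lesser matter of the same kind.

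**What to change.** Add to Treatment Satisfaction/Acceptability: *The same exit interview will be offered when a participant withdraws. Participants who change drink will also be offered it at the change, about the assigned drink, and that rating will be reported separately from the end-of-study rating.*

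Add to the Statistical Analysis Plan: *Acceptability will be summarized by randomized arm, with the number interviewed out of the number randomized.*

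Secondary addition: *Participants who stop taking study beverages will be invited to the scheduled 6-week assessment so that lipids can be measured. They count as non-completers for the 70% retention criterion whether or not they attend.* The last sentence is needed because otherwise returning stoppers could be counted as retained and raise the proportion judged against 70%. This visit should not be described as filling the gap in liver safety data.

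The retention definition, the 70% cutoff and the analysis by assigned arm stay as they are. The cost is a few sentences and a few short interviews and visits by existing staff. Some leavers will decline, and the acceptability figures may come out less favourable.

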This study is a pilot randomized controlled trial where participants are randomized to one of three beverages: Green Tea (GT), Mediterranean lemonade (ML), or a Flavored Water control (FW). Participants will be stratified by gender using block randomization and an allocation ratio of 2:2:1 with variable block sizes. A computer randomization system will be used to complete the randomization assignment. We propose to consent 150 individuals to randomize 50 participants into our 6-week study. Following consent and baseline assessments, randomization assignment will be determined and documented in the participants' study record and shared with the participant. Assessments will be performed by blinded study personnel. Under no circumstances will unblinding be permissible. Investigators, intervention staff, and participants will not be blinded for the study. The schedule of the enrollment, interventions, and assessments according to SPIRIT requirements is shown in **Figure 1**.

Figure 1. Content for the schedule of enrollment, interventions, and assessments according to SPIRIT requirements

	STUDY PERIOD			
	Enrollm ent	Allocation	Post- allocation	Close- out
TIMEPOINT**	$-t_1$	0	t_1	t_x
ENROLLMENT:				
Eligibility screen	X			
Informed consent	X			
2-Week Run-In	X			
Allocation		X		
INTERVENTIONS				
Green Tea			◆—————◆	
Mediterranean Lemonade			◆—————◆	
Flavored Water Control			◆—————◆	
ASSESSMENTS:				
Anthropometry			X	X
Cardiometabolic Measures			X	X
Self-Reported Questionnaires			X	X

Setting of the Human Research

Research activities will take place at the University of Arizona Collaboratory for Metabolic Disease Prevention and Treatment in Tucson, AZ. All procedures have been approved by the University of Arizona Institutional Review Board.

Study Population

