Upon successful completion of baseline assessments and 2-week run-in, participants will be randomized to a beverage assignment. All participants will be advised to consume the entire beverage assigned on a daily basis (rather than save up and consume large amounts on fewer days). At the start of the intervention, participants will be asked to continue avoiding all other sources of tea, lemonade, and citrus, limit coffee consumption to 2 cups/day, avoid all sweetened beverages other than study-provided drinks, consume water ad lib, and avoid alcohol in excess of 1 drink/day for women and 2 drinks/day for men. In addition, participants will be asked to self-monitor their beverage consumption behaviors using a weekly journal to help habitually regulate beverage intake. Participants will be responsible for picking up one week's worth of beverages once per week from the study clinic. Participants will be asked to return any un-consumed beverages during weekly pick-ups; study staff will measure and record any amount not

consumed. Weekly beverage journals will also be collected and new ones distributed for use the following week. Brief in-person interviews or “check-ins” lasting 5-10 minutes will also take place during this time with bilingual study staff. These interviews will follow a script to review beverage-related behaviors and identify and address specific barriers for adherence to study beverage intake.

Retention Strategies

We will use common strategies to enhance participant retention, including: 1) collecting contact information of participants and at least two family members; 2) program reminders; 3) incentives to complete assessments; and 4) contacting participants at their preferred time by their preferred method (i.e. call or text) in their preferred language.

Participant-Reported Tolerance or Toxicities

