Biological Samples

Emerging evidence indicates that genetic variation may impact the efficacy of lifestyle behavioral interventions [2]. Therefore, we will perform a buccal cell collection by using a cytology brush to brush the inside of each cheek for 30 seconds for the extraction of DNA and subsequent genetic analyses. This optional non-invasive, self-collection of buccal cells will occur at one time and will be performed at either the baseline (preferable) or follow-up visit.

Participants also will have the option of allowing the study investigators to store some of the blood that was taken but not used for other tests. This will allow the researchers to derive metabolomics and molecular data that are complementary in obesity research and provide value for enhancing precision care in this health disparate population.

Cardiometabolic Measures

Fasting blood samples (venipuncture; 25 mL), will be collected at baseline and 6-weeks, by a trained phlebotomist, for the purpose of examining the following cardiometabolic measures: total cholesterol, triglycerides, HDL, LDL, very low-density lipoprotein (VLDL), HbA1C, hs-CRP, and fasting glucose. A comprehensive metabolic liver/kidney panel will be performed to assess the following: albumin, globulin, A/G ratio, total protein, alkaline phosphatase, ALT, AST, total bilirubin, blood urea nitrogen (BUN), calcium, creatinine, BUN/creatinine ratio, glomerular filtration rate/estimated, and electrolytes (sodium, potassium, chloride, carbon dioxide). All laboratory tests will be performed by an independent, clinical lab (Banner University Medical Center, Tucson, AZ), blinded to the study outcomes.

Physical Activity

Physical activity will be assessed at baseline and 6-weeks using the Global PA Questionnaire (GPAQ) [3, 4]. It is available in both English and Spanish and provides minutes/week of physical activity of varying intensity and type. The GPAQ has been validated compared to accelerometer data in determining time spent in moderate-to-vigorous physical activity (MVPA) and to assess changes in physical activity over time. Cleland et al. [4] found a moderate agreement between the GPAQ and accelerometer for MVPA mins/day ($r = 0.48$) and results for agreement in change over time showed moderate correlation ($r = 0.52$, $p = 0.12$). Similar correlations have been reported for the GPAQ compared to accelerometer data for Hispanic women participating in a 6-month physical activity intervention [3].

Diet

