considered feasible if the proportion retained is greater than 70%. If retention in the study is 81% or greater, the 95% confidence interval will not contain this 70% cutoff. Power will be insufficient to detect a minimum important difference of a 6 mg/dL change in fasting lipids from baseline, the primary efficacy outcome, based on variance estimates from a trial using a different fruit [14] (standard deviation ≈ 25 mg/dL). We acknowledge that we are not sufficiently powered to detect important differences between arms, but if the 95% confidence intervals for the comparison of the arms contain important differences we will take this as indication of a promising intervention. Variance components estimated from this study will be used to design an adequately powered trial.

Data Management

Data management will be conducted according to Good Clinical Practice guidelines to enhance data quality assurance and control. This will include standard operating procedures and staff trainings for data acquisition, entry, and processing. Further, information obtained from this research will be kept confidential to respect the participant's privacy. All records will be stored and locked in a file cabinet. In addition, all research databases will have password-controlled access, and the researchers will control this access. Data analyses will take place using a dedicated study computer upon study completion. No interim analyses will be performed. Study data will be uniquely coded for each subject and then entered via secure server to a Research Electronic Data Capture (REDCap) database maintained by the Clinical and Translational Sciences Research Center (CATS) at the University of Arizona. Only local study personnel will have access to identified study data. Once the study is complete the study records will be transferred to the University of Arizona storage facility and kept in accordance with applicable

laws. All participant data (including signed informed consent) will be stored for 6 years after the completion of the project. Results from this study will be disseminated through peer-reviewed manuscripts and presentations at national meetings. Participants will be provided with a lay summary of the research findings and the peer reviewed manuscripts.

List of Abbreviations:

Center of Disease Control (CDC)

Body mass index (BMI)

Epigallocatechin gallate (EGCG),

Sugar-sweetened beverages (SSBs)

hs-CRP (high-sensitivity C-reactive protein)

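### The lipid model gives each arm its own baseline mean; adjusting for baseline would cheaply and modestly narrow the arm-comparison CI, provided the SD does not rise between visits

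*Combined protocol and SAP*

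**What the plan says.** The Efficacy Outcomes section of the SAP describes the fixed part of the model for lipids and the secondary blood measures: "We will include fixed effects of intervention arm, time and their interaction to allow for different patterns of change between the arms". The correlation between a participant's two visits is handled by one further component, which the section describes in these words: "as well as a random participant effect to account for the longitudinal nature of the data". On the role of the first measurement, the section then says: "Baseline values of the outcomes will be included in the dependent variable vector". The arm comparison is a contrast of changes from baseline, and the analysis set is defined as follows: "Data from all patients who are randomized will be analyzed in the arm that they were randomized to".

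There are only two lipid measurements per participant. Under Cardiometabolic Measures: "Fasting blood samples (venipuncture; 25 mL), will be collected at baseline and 6-weeks".

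The text places baseline before allocation. Design: "Following consent and baseline assessments, randomization assignment will be determined". Study Intervention: "Upon successful completion of baseline assessments and 2-week run-in, participants will be randomized to a beverage assignment". Figure 1, however, appears to mark the cardiometabolic measures under Post-allocation and Close-out, with no mark before allocation.

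The Sample Size Calculation section concedes low power for lipids and reads efficacy from the intervals: "if the 95% confidence intervals for the comparison of the arms contain important differences we will take this as indication of a promising intervention".

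**The concern.** With three arms and two visits, arm, time and arm-by-time effects fit six free means, one baseline and one 6-week mean per arm. Putting baseline in the outcome vector does not adjust for it while the arm main effect stays in. With complete data, the contrast is simply the difference between arms in mean change. Any chance imbalance at baseline is carried in full into that difference, although randomization says that the underlying baseline means are equal.

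What is at stake is precision. The plan judges preliminary efficacy from the arm-comparison 95% CIs, and a measurement the trial already collects could make them somewhat narrower. No bias is alleged.

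**Working it through.** **Inputs from the documents.** 50 randomized, 2:2:1, so about 20/20/10 (Design). Two lipid visits (Cardiometabolic Measures). SD about 25 mg/dL and an important difference of 6 mg/dL (Sample Size Calculation). The plan does not say whether 25 is the SD of a level or of a change.

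**Assumed, because the documents are silent.** Correlation between visits ρ = 0.5, 0.7, 0.8, 0.9; baseline SD 25; 6-week SD 20, 25, 30 or 35; follow-up complete or 20% missing. The last is close to the 19% loss implied by the plan's 81% retention figure.

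**The plan's own statement.** It gives no lipid CI width or power figure, only that power is insufficient. With SD 25 and a difference of 6, two-sided 5% power is 9.0% for 20 v 10 and 11.5% for 20 v 20. The statement is confirmed.

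**Large sample, equal SD σ, complete data.**
- Planned contrast: variance = 2σ²(1−ρ)(1/n1 + 1/n2).
- Common baseline: variance = σ²(1−ρ²)(1/n1 + 1/n2).
- Width ratio = sqrt((1+ρ)/2) = 0.866, 0.922, 0.949, 0.975.

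**Large sample, equal SD, m of n followed up.**
- Planned: σ²[(1−ρ²)(1/m1 + 1/m2) + (1−ρ)²(1/n1 + 1/n2)].
- Common baseline: the first term only. Participants with baseline alone add nothing to the arm contrast.
- At ρ = 0.5 with 16 v 8 followed up: common-baseline SE = 25 × sqrt(0.75 × 0.1875) = 9.375; planned SE = 25 × sqrt(0.140625 + 0.25 × 0.15) = 10.55; ratio 0.889. For ρ = 0.7, 0.8, 0.9 the ratios are 0.936, 0.958, 0.980.

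**Large sample, unequal SD, complete data.** With r = 6-week SD / baseline SD, ratio = sqrt[r²(1−ρ²)/(1 + r² − 2ρr)]. The gain is nil when ρr = 1.

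**Simulation at n = 50.** Arms 10/20/20, 20,000 trials per cell, normal data, no true effect. The unstructured common-baseline model was computed as ANCOVA in completers. In direct REML fits (3,000 trials per cell, five cells) its arm estimate matched ANCOVA to four decimals. Mean 95% CI width relative to the planned model, beverage v flavored water:

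| 6-week SD | Follow-up | ρ 0.5 | ρ 0.7 | ρ 0.8 | ρ 0.9 |
|---|---|---|---|---|---|
| 25 | complete | 0.876 | 0.933 | 0.960 | 0.986 |
| 25 | 20% missing | 0.903 | 0.950 | 0.973 | 0.994 |
| 30 | complete | 0.944 | 0.994 | 1.010 | 1.000 |
| 30 | 20% missing | 0.980 | 1.017 | 1.027 | 1.011 |
| 35 | complete | 0.982 | 1.011 | 1.001 | 0.931 |
| 35 | 20% missing | 1.025 | 1.041 | 1.023 | 0.944 |

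If the SD falls to 20, intervals are 19% to 24% narrower with complete data. Coverage of the ANCOVA intervals was 0.947 to 0.953 in every cell. The planned model covered equally well with complete data, and 0.941 to 0.945 at SD 35 with 20% missing, which explains part of its narrower width there.

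**In mg/dL.** If 25 is the SD at each visit, the complete-data half-width goes from about 19.4 to 17.0 at ρ = 0.5 and from 8.7 to 8.5 at ρ = 0.9. If 25 is the SD of change, the large-sample half-width is 1.96 × 25 × sqrt(1/20 + 1/10) = 19.0, falling to 16.4 at ρ = 0.5 (× 0.866) and 18.5 at ρ = 0.9 (× 0.975).

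**A half-applied change.** Dropping the arm term but keeping only the random intercept forces one SD on both visits. With complete data, coverage then falls to 0.928–0.933 at 6-week SD 30 and 0.908–0.914 at SD 35. With 20% missing it is 0.925–0.931 and 0.903–0.913.

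**The case against.** The planned model is standard, fully specified and valid, and with complete data its contrast is robust to unequal SDs at the two visits. Preferring a constrained baseline is a choice about efficiency, not the correction of an error. That stands.

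The gain cannot be called usual or free on what the documents give. In the 16 rising-SD cells above, the proposed interval is narrower in only 6; with 20% missing it is wider in 6 of 8. Means also hide what a single trial would see. At equal SD and ρ = 0.7, 0.8, 0.9, a smaller simulation (1,000 trials per cell) found the adjusted interval wider in 10%, 21% and 40% of trials with complete data, and in 26%, 38% and 55% with 20% missing. This also stands, and it limits the claim to a similar or falling SD.

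The change hardly moves the plan's reading of the intervals. With no true effect, equal SD and complete data, the chance that the upper limit exceeds 6 mg/dL goes from 0.911 to 0.902 at ρ = 0.5 and from 0.725 to 0.716 at ρ = 0.9. That is correct, but the intervals are still the plan's only efficacy summary between arms, so modest precision at almost no cost is worth having.

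Kenward-Roger inference itself was not simulated; the widths and coverage come from ANCOVA. Direct REML fits with uncorrected SEs and 1.96 covered only 0.939 to 0.942, hence the call for a small-sample method. The same SAP model governs glucose, HbA1c and hs-CRP. Only normal data at a lipid-like SD were examined, so the figures should not be carried over to those outcomes.

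The Figure 1 point depends on column alignment, which a text copy can lose. The text is consistent that baseline comes first, and the Anthropometry section uses baseline blood pressure to exclude people.

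**Conclusion.** This is a cheap improvement, not an error. The planned contrast forgoes baseline adjustment that randomization justifies. If the SD is similar at both visits, the beverage v flavored water 95% CI would be about 12% to 1% narrower with complete data and 10% to 1% narrower with 20% missing, for assumed correlations of 0.5 to 0.9. If the SD falls, the gain is larger. If it rises, the gain is mostly small or absent, and the interval can be about 1% wider with complete data or up to about 4% wider with 20% missing. The correlation and the visit SDs are assumptions throughout.

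A reader might infer that the planned comparison is biased, that narrowing is assured, or that adjustment rescues power or shrinks the next trial. The documents support none of these. The contrast is valid under randomization. The quantities that decide the gain are not given. If 25 is the SD of change, power for 6 mg/dL moves only from 9.0% to 10.7% at ρ = 0.5, and less at higher correlations. The rule for calling an intervention promising is unaffected.

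**What to change.** In Efficacy Outcomes, before outcome data are examined, prespecify for the arm contrasts one of the following:

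- a model with time and arm-by-time but no arm main effect (one shared baseline mean), an unstructured 2x2 covariance for the two visits in place of the random participant effect, and small-sample degrees of freedom and SEs (for example Kenward-Roger); or
- the near-equivalent ANCOVA of the 6-week value on baseline and arm.

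The first keeps every randomized participant in the model, in line with the plan's statement, but adds essentially no precision over ANCOVA in completers. Do not drop the arm term while keeping only the random intercept, because coverage falls if the SD rises.

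Report the two visit SDs and their correlation from the fitted matrix for planning the next trial. Keep within-arm changes as descriptive summaries, since a shared baseline redefines them. State that baseline lipids are drawn before allocation, and reconcile Figure 1 with the Design and Study Intervention text.

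Cost: one SAP sentence, one figure correction, about one degree of freedom and a possible slight widening. No new data or visits are needed.
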